Lead Research Nurse	[name] c/o Surrey CTU (see above) Email: [contact]
Lead Health Economist	[name] c/o University of Surrey (see above) Email: [contact]

i. LIST of CONTENTS

GENERAL INFORMATION	Page No.
TITLE PAGE	1
RESEARCH REFERENCE NUMBERS	2
SIGNATURE PAGE	3
KEY TRIAL CONTACTS	4
i. LIST of CONTENTS	5
ii. LIST OF ABBREVIATIONS	6
iii. TRIAL SUMMARY	7
iv. TRIAL FLOW CHART	8
v. ROLES & RESPONSIBILITIES OF TRIAL MANAGEMENT COMMITTEES, GROUPS AND INDIVIDUALS	9
SECTION	
1. BACKGROUND	10
2. RATIONALE	11
3. OBJECTIVES AND OUTCOME MEASURES/ENDPOINTS	12
4. TRIAL DESIGN	15
5. TRIAL SETTING	17
6. PARTICIPANT ELIGIBILITY CRITERIA	17
7. TRIAL PROCEDURES	18
8. TRIAL TREATMENTS	24
9. PHARMACOVIGILANCE	27
10. STATISTICS AND DATA ANALYSIS	30
11. DATA MANAGEMENT	35
12. RISK ASSESSMENT & MONITORING	36
13. ETHICAL AND REGULATORY CONSIDERATIONS	38
14. DISSEMINATION	44
15. REFERENCES	45
16. APPENDICES	49

ii. LIST OF ABBREVIATIONS

AE	Adverse Event
ADRT	Advance Directive to Refuse Treatment
CAH	Clinically-Assisted Hydration
CI	Chief Investigator
CRF	Case Report Form
CRM	Cluster Representation Mechanism
CRT	Cluster Randomised Trial
CTA	Clinical Trial Authorisation
CTIMP	Clinical Trial of Investigational Medicinal Product
CTU	Clinical Trials Unit
DMEC	Data Monitoring & Ethics Committee
GCP	Good Clinical Practice
HRA	Health Research Authorisation
ICMJE	International Committee of Medical Journal Editors
IRAS	Integrated Research Application System
ISF	Investigator Site File
ISRCTN	International Standard Randomised Controlled Trials number
MAR	Missing at Random
MDT	Multidisciplinary Team
MHRA	Medicines and Healthcare products Regulatory Agency
m-RASS	Modified Richmond Agitation and Sedation Scale
NHS	National Health Service
NICE	National Institute for Health and Care Excellence
NIHR	National Institute for Health Research
Nu-DESC	Nursing Delirium Screening Scale
PI	Principal Investigator
PIS	Participant Information Sheet
PPI	Public and Patient Involvement
QC	Quality Control
RCT	Randomised Control Trial
R&D	Research & Development
REC	Research Ethics Committee
SAE	Serious Adverse Event
SAP	Statistical Analysis Plan
SOP	Standard Operating Procedure
TMG	Trial Management Group
TSC	Trial Steering Committee

iii. TRIAL SUMMARY

Trial Title	A cluster randomised trial of clinically-assisted hydration in patients in the last days of life	
Internal ref. no. (or short title)	CHELsea II trial	
Clinical Phase	Phase III trial	
Trial Design	Cluster randomised trial	
Trial Participants	Patients in last days of life (< 7 days)	
Planned Sample Size	1600 participants	
Treatment duration	14 days (maximum)	
Follow up duration	n/a	
Planned trial period	October 2022-September 2024	
	Objectives	Outcome Measures
Primary	Prevalence of delirium	Nursing Delirium Screening Scale
Secondary	Level of sedation	Modified Richmond Agitation and Sedation Scale
	Prevalence of audible upper airway secretions	Clinical observation
	Prevalence of pain, shortness of breath, nausea & vomiting	Clinical observation
	Overall survival	Clinical observation
	Adverse effects (clinically-assisted hydration)	Clinical observation
	Health economic analysis	Resource utilisation
	Clinically-assisted hydration plus usual end-of-life care interventions (versus solely usual end-of-life care interventions)	
Intervention	Fluid type: 4% dextrose 0.18% sodium chloride Fluid volume: variable (weight dependent) Route of administration: intravenous or subcutaneous	
Formulation, dose, route of administration		

iv. TRIAL FLOW CHART

[figure not shown]

Figure 1 – Trial Flow Chart.

v. ROLES AND RESPONSIBILITIES OF TRIAL MANAGEMENT COMMITTEES/GROUPS & INDIVIDUALS

The trial will be coordinated by Surrey Clinical Trials Unit (based within the University of Surrey) and will be sponsored by the University of Surrey.

The trial will have a Trial Management Group (TMG), which will oversee the day-to-day management of the trial. The TMG will formally meet at least monthly (i.e., whole group), but will informally meet as often as necessary (i.e., specific members). The TMG will include [name] (Chief Investigator), [name] (Director of Surrey CTU), [name] (Senior Research Nurse), [name] (Clinical Project Manager of Surrey CTU), and dedicated Surrey CTU staff. The TMG will receive input from the Trial Steering Committee (TSC), and the Data Monitoring and Ethics Committee (DMEC) and will provide necessary feedback to the sponsor of the trial, the funder of the trial, the regulatory authorities, and the Principal Investigators (PIs)/research sites.

The trial will have a TSC, and its constitution, composition and function will follow the National Institute for Health Research (NIHR) research governance guidelines [1]. The primary role of the TSC is "to provide overall supervision for a project on behalf of the Project Sponsor and Project Funder and to ensure that the project is conducted to the rigorous standards set out in the Department of Health's Research Governance Framework for Health and Social Care and the Guidelines for Good Clinical Practice". The TSC will include the following members: a) independent chair; b) independent clinician (palliative medicine consultant); c) independent statistician; d) public and patient involvement (PPI) representative(s); e) member of TMG (non-voting); f) sponsor representative (observer); g) local Cancer Research Network representative (observer). The TSC will meet at least every 6 months, and the meetings will be scheduled following the DMEC meetings (in order for the TSC to review the DMEC feedback). The TSC will provide a report for the Sponsor, the Funder, and the Project Management Group. (The report will also be sent to the PIs and the DMEC).

The trial will have a DMEC, and its constitution, composition and function will follow the NIHR research governance guidelines [1]. The primary role of the DMEC is "to monitor the data and make recommendations to the Trial Steering Committee on whether there are any ethical or safety reasons why the trial should not continue". The DMEC will include the following members: a) independent chair (non-medical); b) independent clinician (palliative medicine consultant); c) independent statistician; and d) independent medical ethicist. The DMEC will meet at least every 6 months, and the meetings will be scheduled before the TSC meetings (in

order for the TSC to review the DMEC feedback). The DMEC will provide a report for the TMC, the Sponsor, the Funder, and the Project Management Group. (The report will also be sent to the PIs).

1 BACKGROUND

The provision of clinically-assisted hydration (CAH) at the end-of-life is one of the most contentious issues in medicine, and indeed within the general population [2]. The reasons for contention include: a) the lack of evidence for/against CAH [3,4]; b) the disparate opinions of healthcare professionals about CAH [4]; and c) the generally positive opinions of patients and their carers about CAH (and the generally negative opinions about withholding/withdrawing CAH) [5,6] It is, therefore, unsurprising that the provision of CAH at the end-of-life is extremely variable within clinical practice (e.g., 12-88% cancer patients in the last week of life) [7].

The CHELsea II trial is a cluster randomised trial of standard end-of-life care with CAH (versus standard end-of-life care without CAH) in patients in the last days of life. The CHELsea II trial (definitive trial) leads on from the Research for Patient Benefit (RfPB) - funded CHELsea I trial (feasibility trial) [8,9], which achieved all of the pre-defined criteria for success, and especially the recruitment criterion (i.e., 200 patients from 12 trial sites in one year) [9]. It should be noted that the feasibility trial only included patients with cancer, but (on the basis of feedback from the HTA Funding Committee) the definitive trial will include patients with cancer and patients with non-malignant disease.

The Cochrane review of medically assisted hydration (aka CAH) for adult palliative care patients concluded that “there are insufficient good-quality studies to make any definitive recommendations. As a result, it is not possible to define the benefits and harms of this treatment clearly” [3]. It identified 6 relevant studies, although only 3 studies were randomised controlled trials (RCTs) [10-12]. However, none of the RCTs addressed the specific issue of the routine use of CAH at the end-of-life.

Thus, Cerchietti et al (2000) included patients with evidence of dehydration (and/or renal failure), and the fluids were only given for 48 hours (and not continued until death) [10]; Bruera et al (2005) only included patients with evidence of dehydration, and the fluids were only continued for 48 hours (and not continued until death) [11]; and Bruera et al (2013) only included patients with evidence of dehydration, and the fluids were continued for a variable duration, i.e., “until the patient was unresponsive, developed progressive coma, or died” [12].

These RCTs used low volumes of fluid (1 L/day), even though many of the patients were clinically dehydrated. On the basis of the National Institute for Health and Care Excellence (NICE) clinical guidance on intravenous fluid therapy in adults in hospital [13], 1 L/day would be an appropriate volume for maintenance in a non-dehydrated patient weighing only 33-40 kg and would be an inappropriate volume for treatment in a dehydrated patient of any weight. [Recommended maintenance intravenous fluid therapy is 25-30 mL/kg/day of water (with appropriate amounts of sodium, potassium, chloride, and glucose)] [14].

The CHELsea II trial will uniquely address the specific issue of the “routine” use of CAH at the end-of-life: the CHELsea II trial will involve a clinically relevant population (i.e., hydrated patients), an appropriate intervention (i.e., “maintenance” volumes of parenteral fluids), a more relevant follow up period (i.e., until death), and a clinically relevant primary endpoint (i.e., delirium). Thus, the CHELsea trial will provide an evidence-base for the routine use of CAH at the end-of-life.

Delirium is one of the most common problems (25-85% patients) [14], and one of the most distressing problems [15], at the end-of-life. There are three subtypes of delirium: 1) hyperactive (agitated); 2) hypoactive (lethargic); and 3) mixed [16]. The clinical features of delirium are variable, but the two “essential concepts” are disordered attention (arousal), and disordered cognition [16]. Hyperactive delirium is associated with agitation, disorientation, delusions, and hallucinations (and is especially distressing for patients, relatives, and healthcare professionals) [15].

Dehydration is a recognised cause of delirium, and rehydration is a recommended intervention for delirium (in appropriate situations) [14]. However, the mainstay of the management is the use of antipsychotics and/or benzodiazepines [14]. Such drugs are used in ~50% patients in the last week of life [17], and although they are generally effective, they are often associated with untoward sedation (which necessarily impacts on the dying process, especially in terms of interpersonal communication).

2 RATIONALE

As discussed, the provision of CAH at the end-of-life is one of the most contentious issues in medicine. The “issue” is not new [18], and the debate primarily continues due to the lack of evidence for/against CAH [3,4]. Recently, the “issue” has received greater attention due to the widespread negative publicity about the Liverpool Care Pathway (LCP), and the subsequent Neuberger review of the LCP (which resulted in withdrawal of the LCP in the UK) [2].

The Neuberger review noted that “most of the submissions to the Review from relatives and carers that were critical of the LCP made reference to hydration and nutrition” [2]. Moreover, the Neuberger review comments that “if fluids are stopped without review over many days, death from dehydration will be inevitable, the lack of hydration having accelerated the dying process” [2]. It should be noted that the Neuberger review also highlighted concerns about the use of sedative drugs at the end-of-life (see above).

Data from recent national audits of end-of-life care in hospitals in the UK suggests that there has been an increase in the number of patients receiving CAH in the last days of life [19,20]. Thus, 29% patients were receiving CAH “at the time of the patient’s death” in 2013, whilst 43% patients were receiving CAH “in the last 24 hours before the patient’s death” in 2016 [20]. This major change in practice does not relate to any new evidence (or, indeed, any new guidance), and undoubtedly reflects the widespread negative publicity around the LCP, and specifically the negative publicity around withholding/withdrawing CAH at the end-of-life [2].

In terms of guidance, the NICE guideline on care of dying adults in the last days of life states that healthcare professionals should “discuss the risks and benefits of clinically assisted hydration with the dying person and those important to them” [21]. However, the NICE guideline highlights the lack of evidence on CAH (in order to do so): “clinically assisted hydration may relieve distressing symptoms or signs related to dehydration but may cause other problems”; “it is uncertain if giving clinically assisted hydration will prolong life or extend the dying process”; “it is uncertain if not giving clinically assisted hydration will hasten death” [21].

Thus, there has been a need for further research for some time, but recent events (and the resultant change in clinical practice despite no change in research evidence) has intensified the need for a robust (adequately powered) trial of CAH at the end-of-life. Moreover, the successful completion of the CHELsea I trial [9], which achieved all of its predetermined criteria for success, supports the undertaking of such a trial (utilising a cluster randomised trial design).

The trial will also facilitate the Consortium for Hospice and Community Research (which includes the NIHR) objective to increase the number of hospices recruiting to NIHR CRN portfolio studies [22]. Thus, the trial will recruit 1600 patients from 80 sites within the UK (predominantly inpatient hospices).

3 OBJECTIVES AND OUTCOME MEASURES/ENDPOINTS

Our hypothesis is that CAH in the last days of life reduces the prevalence of delirium (and the requirement for sedative medication), as a result of preservation of renal function, and

prevention of build-up of drugs and toxins. Furthermore, CAH will prevent death due to dehydration occurring before death due to the underlying disease (or its complications).

The aim of this cluster randomised trial is to fully evaluate CAH in patients in the last days of life. The primary objective is to assess the effect of CAH on prevalence of delirium. The secondary objectives are to assess the: a) effect of CAH on prevalence of audible upper airway secretions ("death rattle"); b) effect of CAH on prevalence of pain and other symptoms (shortness of breath, nausea and vomiting); c) tolerability of CAH; d) effect of CAH on survival; e) health economic impact of CAH; and f) differences in response to CAH between participants with cancer and participants with non-malignant disease.

3.1 Primary endpoint/outcome

The primary endpoint is the proportion of participants that develop delirium at any point during the trial. The Nursing Delirium Screening Scale (Nu-DESC) will be used to identify participants with delirium: the Nu-DESC is a validated, five item screening tool for delirium (Table 1) [23], which is endorsed for use at the end of life [24], and which was utilised in a recent Australian, multicentre, phase 2, CRT of a multimodal intervention to prevent delirium in participants with advanced cancer [25]. The Nu-DESC will be completed as part of the regular four hourly assessment of participants, and also when a participant is administered either "as-required" or regular medication for delirium (unless the latter relates to the regular four hourly assessment of the participant). Each "feature" on the Nu-DESC is rated from 0-2 (where 0 = absent, and 2 = severe), and a total score of >1 is indicative of delirium (although a total score of > 0 has a higher sensitivity with a similar specificity) [26]. A cut-off of > 1 is more clinically relevant (for a trial involving patients in the last days of life), and a score of > 1 in domain 5 / psychomotor retardation is indicative of hypoactive delirium (vs. hyperactive delirium).

3.2 Secondary endpoints/outcomes

The secondary endpoints are:

- ❖ Proportion of participants with Nu-DESC total score of > 0 at any point during the trial.
- ❖ Nu-DESC scores during trial (mean score during the trial; proportion time with score 0; proportion time with score > 0; proportion of time with score > 1).
- ❖ Time to first episode of Nu-DESC score > 1.
- ❖ Proportion of participants that receive as-required and/or regular medication specifically for delirium at any point during the trial (data derived from drug chart).

- ❖ Time to first dose of medication for delirium (as-required or regular – data derived from drug chart).
- ❖ Modified Richmond Agitation and Sedation Scale (m-RASS) scores during trial (mean score during the trial; proportion time with score 0; proportion time with score 0 to -2 – data derived from clinical observation document). The RASS is a validated measuring tool for severity of agitation and level of sedation, and the m-RASS has been modified for/validated in patients with advanced cancer (Table 2) [27].
- ❖ Proportion of participants with audible upper airway secretions at any point during the trial (“death rattle” – data derived from clinical observation document).
- ❖ Time to first episode of audible upper airway secretions.
- ❖ Proportion of participants that receive as-required and/or regular medication specifically for audible upper airway secretions at any point during the trial (data derived from drug chart).
- ❖ Time to first dose of medication for audible upper airway secretions (as-required or regular – data derived from drug chart).
- ❖ Proportion of participants that experience pain, shortness of breath, and nausea and vomiting (and require medication for these symptoms – data derived from clinical observation document and drug chart).
- ❖ Adverse effects of CAH, e.g., peripheral oedema, pulmonary oedema, cannula site inflammation, cannula site infection. (Data derived from clinical observation document)
- ❖ Overall survival (data derived from clinical observation document). Participants that survive >14 days will continue to be followed up in order to determine their date of death.
- ❖ Participant level costs (data derived from clinical observation document and drug chart) and cost effectiveness based on reductions in the likelihood of delirium.
- ❖ Carer feedback on end-of-life care and research participation – Carers will be asked to complete a survey based on the Quality Survey developed by the National Audit of Care at the End of Life (NHS Benchmarking Network) in conjunction with the Patients Association [28]. In addition to the standard questions relating to end-of-life care, we will include specific questions about the research project. The survey will be sent out 8 weeks after the participant’s death (as in the National Audit of Care at the End of Life).

Features and description	Symptom rating
1. Disorientation Verbal or behavioural manifestation of not being oriented to time or place or misperceiving persons in the environment	0 – absent 1 – present but not severe 2 – severe
2. Inappropriate behaviour Behaviour inappropriate to place and/or for the person; e.g., pulling at tubes or dressings, attempting to get out of bed when that is contraindicated, and the like	0 – absent 1 – present but not severe 2 – severe
3. Inappropriate communication Communication inappropriate to place and/or for the person; e.g., incoherence, non-communicativeness, nonsensical or unintelligible speech	0 – absent 1 – present but not severe 2 – severe
4. Illusions / hallucinations Seeing or hearing things that are not there; distortions of visual objects	0 – absent 1 – present but not severe 2 – severe
5. Psychomotor retardation Delayed responsiveness, few or no spontaneous actions/words; e.g., when the patient is prodded, reaction is deferred and/or the patient is unarousable	0 – absent 1 – present but not severe 2 – severe
Total score	

Table 1 – Nursing Delirium Screening Scale (Nu-DESC) [23].

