6.2 Exclusion criteria

The exclusion criteria are:

- a) patient is dehydrated (guidance on indicators of dehydration in Appendix 5)
- b) patient has a relevant Advance Directive to Refuse Treatment (ADRT)
- c) clinical indication for CAH
- d) clinical contraindication to CAH
- e) contraindication to cannulation
- f) total parenteral nutrition/enteral feeding in situ
- g) patient has had delirium in last 24 hours
- h) patient has had audible upper airway secretions in last 24 hours
- i) patient likely to be transferred elsewhere for end-of-life care
- j) patient has clinically significant cardiac failure as deemed by clinical team (see criteria "d")

- k) patient has clinically significant renal failure as deemed by clinical team (see criteria "d")
- l) patient has clinically significant dementia as deemed by clinical team (potential false positives on delirium screening)

Patients that are dehydrated will be eligible for inclusion after correction of dehydration has occurred.

Patients in research sites that are randomised to Standard intervention B, who are already receiving CAH, are eligible to take part in the trial (assuming they meet the other inclusion criteria). However, ongoing CAH must be given as per the protocol

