7.7 Long term follow-up assessments

Participants that survive >14 days will continue to be followed up in order to determine their date of death (but there will be no other trial-related assessments during this period).

ASSESSMENT	ENTRY TRIAL	DURING TRIAL (4 HOURLY ASSESSMENTS)	END TRIAL
Demographic information	✓		
Regular medication	✓	✓	
As-required medication	✓	✓	
Fluid intake		✓	
Urinary output		✓	
NuDESC score		✓	
m-RASS score		✓	
Presence of audible upper respiratory secretions		✓	
Presence of symptoms		✓	
Adverse effects (CAH)		✓	
Trial outcome			✓
Overall survival			✓

Table 3 – Summary of trial assessments.

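### Four secondary medication endpoints count regular treatment already running at entry as a trial event, which dilutes any effect of CAH on new need for treatment

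*Protocol*

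**What the plan says.** Section 3.2 of the protocol lists four secondary endpoints on medication:

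- delirium, proportion: "Proportion of participants that receive as-required and/or regular medication specifically for delirium at any point during the trial"
- delirium, time: "Time to first dose of medication for delirium (as-required or regular", from the drug chart)
- secretions, proportion: "Proportion of participants that receive as-required and/or regular medication specifically for audible upper airway secretions at any point during the trial"
- secretions, time: "Time to first dose of medication for audible upper airway secretions (as-required or regular", from the drug chart)

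All four expressly include regular medication, and none requires the drug to have been started after entry.

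Two exclusion criteria in section 6.2 bear on this: "patient has had delirium in last 24 hours" and "patient has had audible upper airway secretions in last 24 hours". Both describe the symptom. No criterion mentions current treatment for either problem.

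Table 3 (section 7.7) has a row "Regular medication", and another for as-required drugs, each ticked at entry and during the trial. Section 7.6 has the clinical team record medications and their indications during the trial. The baseline lists in sections 7.5 and 10.3.1 do not include treatment at entry, nor do the model covariates in sections 10.3.2 and 10.5.

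**The concern.** Section 3 states the hypothesis that CAH lowers the prevalence of delirium and the need for sedative drugs. An endpoint that tests the second part should register need that arises once the participant is under observation. As written, these endpoints also register treatment that is merely continued.

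Take a participant whose delirium settled two days before entry on a regular drug still charted for delirium. The 24-hour criterion is met. The next routine dose makes this participant an event for the proportion endpoint and sets the time to first dose close to zero. Hydration cannot change either result. The same reasoning applies to a regular antisecretory drug and the two secretions endpoints.

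The primary endpoint concerns participants who develop delirium and is paired with a delirium-free window at entry. The medication endpoints have no matching treatment-free condition. What is at stake is the sensitivity and interpretation of four secondary endpoints.

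**Working it through.** **The plan's own figure.** The protocol gives no sample size or power for the medication endpoints, so the primary calculation in section 10.1 serves as a yardstick. Two proportions of 60% and 50%, 90% power and two-sided alpha 0.05 give 519 per arm, 1038 in total, which matches the protocol. (Section 10.1 prints alpha as 0.5. Only 0.05, the level in section 10.3.2, reproduces 1038.) The design effect is 1 + 19 × 0.025 = 1.475, and 1038 × 1.475 = 1531. Dividing by 0.95 gives 1612, close to the stated 1600. The effective size per arm is 1600 × 0.95 / 1.475 / 2 = 515.

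**Dilution.** Let f be the share already on regular treatment for the indication at entry, equal in both arms, and p the event rate among the others. Under the present wording each arm's rate is f + (1-f)p, so the arm difference is (1-f)d. Neither f nor p is in the documents. The 60% and 50% below are borrowed from the primary endpoint.

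| f (assumed) | Arm rates | Difference | Power at 515 per arm |
|---|---|---|---|
| 0 | 60.0% v 50.0% | 10.0 | 90% |
| 5% | 62.0% v 52.5% | 9.5 | 87% |
| 10% | 64.0% v 55.0% | 9.0 | 84% |
| 15% | 66.0% v 57.5% | 8.5 | 80% |
| 20% | 68.0% v 60.0% | 8.0 | 76% |

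The shrinkage factor does not depend on p. With 50% v 40% and f = 15%, the rates are 0.15 + 0.85 × 0.50 = 57.5% and 0.15 + 0.85 × 0.40 = 49.0%, again 8.5 points apart.

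**What a change of definition recovers.** Restricting to participants untreated at entry restores the full d with fewer participants. At f = 20% the mean cluster is 16, the design effect is 1 + 15 × 0.025 = 1.375, and the effective size is 1600 × 0.95 × 0.80 / 1.375 / 2 = 442 per arm. Power for 60% v 50% is then about 85%, against 76% for the any-use definition. If everyone is kept but only new treatment counts, the result depends on those already treated. The full d returns if they need new treatment as often as the others and respond alike. If none of them ever does, the rates are (1-f)p and the difference is again (1-f)d. This is why both analyses are worth showing.

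**Imbalance between arms.** If f were 20% in one arm and 10% in the other, with p = 50% in both, the endpoint would read 0.20 + 0.80 × 0.50 = 60% against 0.10 + 0.90 × 0.50 = 55% with no effect of CAH. To judge how likely that is by chance, assume a mean f of 15% and 40 sites of 20 per arm. The standard error of the arm difference in f is √(2 × 0.15 × 0.85 × 1.475 / 800) = 2.2 points at ICC 0.025. It is 2.5 points at ICC 0.05 and 3.0 at ICC 0.10. A 10-point gap is about 4.6, 4.0 and 3.3 standard errors respectively.

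**The case against.** **This belongs in the SAP.** Section 10.3 promises a full SAP, and derivation rules for secondary endpoints often sit there. That would answer a gap. Here the protocol states a rule: regular medication counts, at any point in the trial. An SAP limited to new starts would alter that endpoint, so it is better to correct the wording.

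**The affected group is inferred.** The protocol does not say whether a patient controlled on treatment counts as free of delirium under the exclusion, and it names no assessment tool for that criterion. Eligibility is the natural reading of a symptom-based rule but is not stated, and the number affected is unknown. The figure of about 50% in section 1 is use of antipsychotics or benzodiazepines during the last week of life. It is not use for delirium at entry and cannot stand in for f. This objection stands as a limit on size.

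**Total use is a fair measure of drug requirement.** It is, and it deserves to be kept as a sensitivity analysis. It answers a different question from whether CAH prevents new need.

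**A stronger reading.** A reader might infer that unequal treatment at entry would create a false difference between arms, because prescribing habits vary by site. The documents do not support assuming this. Sites are randomised 1:1, and chance variation between sites would rarely produce a gap as large as the one illustrated above. The random effect for centre is there to carry such variation. Selective recruitment in an unblinded cluster trial is a separate route, possible but not shown by anything in the protocol.

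**Removing participants already treated.** Dropping them from the main analysis would depart from section 10.7, which includes all observed data by allocation. Allocation also sets the site's standard of care, and section 6.2 lets patients already on CAH enter at intervention B sites. Treatment at entry may therefore partly reflect allocation, and conditioning on it in the main analysis would be unwise. This objection stands and shapes the fix.

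**Conclusion.** The point holds for the four secondary medication endpoints. As worded, continuation of a regular drug already charted for delirium or secretions at entry is an event near time zero that CAH cannot prevent, and any arm difference shrinks by the factor (1-f). For an assumed f of 5% to 20%, 10 points becomes 9.5 to 8.0. Illustrative power falls from 90% to between 87% and 76%, using rates borrowed from the primary endpoint. The algebra is exact for equal f in both arms. The values of f and p are assumptions.

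Two wider conclusions do not follow. Not every regular drug counts, since the endpoints cover only medication given specifically for the indication. The primary endpoint is not affected either, because it rests on the Nu-DESC score and a dose alone does not make a primary event. Arm imbalance in treatment at entry is a secondary matter, to be checked in the data and not presumed.

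**What to change.** Reword the four endpoints so that the event is medication for that indication newly started after entry, or a first as-required dose given after entry. Continuing a regular drug already charted for the indication at entry would not count. Then:

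- keep all participants in the intention-to-treat set for the main analysis of these endpoints;
- report by arm the proportion on such medication at entry, from the Table 3 entry record;
- show two sensitivity analyses: the protocol's present any-use definition, and an analysis restricted to participants not on such medication at entry.

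Settle this before the first unblinded efficacy analysis.

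The cost is modest. Medication at entry is already recorded, and no participant's care changes. Derivation takes somewhat more work. The indication of drugs charted at entry must be confirmed, because section 7.6 records indications during the trial and Table 3 does not say they are captured at entry. The restricted analysis has fewer participants and should carry a caution that treatment at entry may itself reflect site allocation.
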